## 11.1.2 Brief Motivational Interventions to Promote Health Behaviour

Health behaviour theories are frequently used to design brief psychological interventions to promote positive health behaviour change or to motivate patients to attend a health care service, because interventions based on a theoretical framework are considered most effective (Michie et al., 2008). Volitional help sheets draw on the transtheoretical model of change (Prochaska and DiClemente, 1983) to provide a means by which individuals can generate their own behaviour implementation intentions to help them move from inaction to action. Provision of a volitional help sheet has been found to successfully reduce cigarette smoking (Armitage, 2008), alcohol consumption (Armitage and Arden, 2012), and suicidal ideation and behaviour (Armitage et al., 2016, O'Connor et al., 2017).

Motivational letters guided by principles of Motivational Interviewing (Rollnick and Miller, 1995, Miller and Rollnick, 2012) have been found to successfully promote a range of health-related behaviours including attendance to psychological treatment for gambling disorder (Pfund et al., 2020), cardiac rehabilitation enrolment and attendance (Pfund et al., 2020, Mosleh et al., 2014, Wyer et al., 2001), and cancer screening uptake (Chan and So, 2021). They are often used because they are considered low-risk and require lower amounts of time, effort, and money to deliver, while providing the potential for considerable health gains (Dressler et al., 2012).

A study exploring how concepts from the Theory of Planned Behaviour (TPB) (Ajzen, 2011) are operationalised in the design of motivational letters of invitation to cardiac rehabilitation highlighted the importance of relatable and personal messaging, and the use of the future tense in sentences to motivate patients to engage in future behaviour (Dressler, 2018). The findings were related to the subjective norm, perceived control, and attitude components of the TPB, which together are involved in the process from intention to behaviour. Firstly, both letters reviewed in the study were related to subjective norm component by writing about what the doctor or other health care professional expected of patients regarding cardiac rehabilitation. Secondly, perceived control was reflected in the provision of information about what cardiac rehabilitation is. Finally, attitude was operationalised through language that conveyed a positive outlook, emphasised the importance of engaging in the target behaviour, and explicitly stated how negative consequences of not engaging in the target behaviour can be avoided.

When designing interventions to promote behaviour change, it is important to specify the target behaviour to be changed and to identify what needs to change in the person and/or the environment to achieve the desired behaviour change. The COM-B model proposes that for any behaviour to occur, the person must have the capability to perform the behaviour (e.g., strengths, knowledge, skills), there must be the opportunity for the behaviour to occur (i.e., accessibility, affordability, social acceptability, time), and there must be sufficient motivation to either do the behaviour or not to engage in a competing behaviour (Michie et al., 2014). Therefore, the content in the motivational letter used in the present study will seek to promote the key areas of participants' capability, opportunity, and motivation.

Children's stories can be effective as oral health promotion interventions. O'Malley and colleagues developed a storybook intervention called 'Kitten's First Tooth' (KFT) using established behaviour change techniques (O'Malley et al., 2017). The intervention was effective in increasing parental self-efficacy and parent intention for their child to attend the dentist. The present study will use the KFT storybook as part of a family oral health toolkit (including information on how to access an audio version of KFT online, toothbrush, and toothpaste) in addition to a motivational letter to promote attendance to a dental check-up in irregular dental-attending children while also providing an opportunity to enhance recruitment to the CHOICE Trial.

### 11.1.3 Methodology

### 11.1.3.1 Aims and Objectives

The CHOICE Trial will enhance its recruitment strategy from the outset to include a motivational letter and family oral health toolkit to promote engagement of harder to reach families (i.e., those who are none or irregular dental attenders) via a primary school and nursery school outreach programme for children aged 4 to 7 years, that is, children attending nursery and primary school; initiated by dental nurses from the CHOICE general dental practices during the first 18 months of recruitment.

The research questions are,

- 1. Does a motivational letter and oral health toolkit intervention enhance recruitment to the CHOICE Trial in irregular dental-attending children?
- 2. What are the facilitators and barriers to recruitment of the target population?

### 11.1.3.2 Participants

Participants will be parent's/primary caregivers and their child aged 4 to 7 years of age attending nursery or primary school in four regions of the U.K. who self-identify as not currently having a dentist for their child. (The North West of England; East of England; Yorkshire and the Humber; Northern Ireland). This will be established by sending a motivational letter home from school providing information on how to get registered with a local CHOICE dental practice if their child does not currently have one. Approximately half of the schools will receive intervention 1, and half will receive intervention 2 (based on recruitment targets). The recruitment strategy will involve dental nurses engaging with around 36 schools within the catchment area of 18 CHOICE dental practices who agree to take part in the SWAT. Given the goal here is to identify children who don't currently have a dentist and enhance recruitment of them to the CHOICE trial, no specific sample size is calculated.

#### 11.1.3.3 Design

- INTERVENTION 1: Parent's/primary caregivers of potential participants will be sent a motivational letter and a voucher for a family oral health toolkit (containing Kitten's First tooth storybook, toothbrush, toothpaste) to be redeemed at the first dental visit for each child. This will be delivered to home via school with the motivational letter for parents/primary caregiver encouraging a visit for a dental check-up.
- INTERVENTION 2: Parent's/primary caregivers of potential participants will be sent a motivational letter to encourage attendance for a dental check-up.

#### 11.1.3.4 Procedure

For research question 1: the 18 CHOICE dental practices across each of the four regions will engage with two local nursery/primary schools within the local area. Potential participants in one of the schools will receive the motivational letter and a voucher for a family oral health toolkit, and those in another school will receive only the motivational letter. Potential eligible participants will be invited to participate in the CHOICE trial in addition to receiving routine dental care. Those in receipt of the oral health toolkit voucher at the dental appointment can exchange the voucher for the free oral health toolkit, which will be recorded by the dental practices. All quantitative data will be anonymised and collected by the dental practices then sent to the LCTC for analysis.

For research question 2: parents/primary caregivers who consent to take part in an interview will be asked about the things that helped them decide whether to take part in the CHOICE trial. Participants will be invited to attend a short online focus group with other primary caregivers of 3–7-year-old children who were invited to participate. The interview will be developed using the Behaviour Change Wheel (COM-B). The interview will explore participants' capability, opportunity, and motivation, to engage in the target behaviour of dental check-up attendance and agreement to enter the CHOICE Trial.

#### 11.1.3.5 Motivational Letter and Family Oral Health Toolkit

The one-page motivational letter will be developed using the Behaviour Change Wheel (Michie et al., 2011) and will promote participants' capability, opportunity, and motivation, to engage in the target behaviour of dental check-up attendance and agreement to enter the CHOICE Trial.

The redeemable voucher can be exchanged for a Family Oral Health Toolkit, consisting of a physical copy of, and weblink to, the Kitten's First Tooth video storybook (O'Malley et al., 2017) and a toothbrush and toothpaste.

#### 11.1.3.6 Analysis

Primary analysis will be a comparison of attendance for a dental check-up and consent/recruitment into the CHOICE Trial. The following outcome measures will be assessed, grouped by intervention:

a) Response rate of attendance for a dental check-up in potential participants who are none or irregular attenders.

b) Proportion of potential participants who consent to take part and are recruited into the CHOICE trial.

In addition, the interviews will be analysed using Reflexive Thematic Analysis (Braun and Clarke., 2019).

#### 11.2 ENCOURAGE sub-study

#### 11.2.1 Rationale:

The ENCOURAGE sub-study is an EME Mechanistic study embedded into CHOICE It is funded by the NIHR EME programme (NIHR151317). Encourage will investigate the biological mechanism of the DR-BNI intervention in CHOICE. There is strong evidence that twice-daily tooth brushing with a fluoride toothpaste is effective in the prevention of

childhood caries (Mejàre et al., 2015). Tooth brushing also aids removal of dental plaque bacteria and facilitates removal of foodstuffs (sugars) that adhere to the teeth where they can be metabolised to acids by plaque bacteria. Effective twice-daily tooth brushing with fluoride toothpaste supports maintenance of the oral microbiome in a beneficial (eubiotic) state (Twetman, 2018). However, families, especially those from poorer socio-economic backgrounds, who face many life challenges, struggle to prioritise oral hygiene over other more pressing needs.

Understanding the biological mechanism of action of the DR-BNI would facilitate objective monitoring of adherence to caries prevention goals (sugar control, oral hygiene). In turn this would obviate the need for unreliable food diaries and may predict future caries at a much earlier stage than waiting for new carious lesions to appear. Caries is a lengthy process in which the tooth enamel and then the underlying dentine is demineralised by acids produced by fermentation of dietary sugars by plaque bacteria. Caries is often associated exclusively with the carious lesion or cavity. However, the caries process is more accurately described as a continuum of many cycles of tooth demineralisation and remineralisation. Demineralisation begins at the atomic level at the crystal surface inside the enamel or dentine and can continue, unless halted, until a cavity is formed (Featherstone, 2008). During the early stages of caries development the process of demineralisation could be halted and remineralisation encouraged, if the causative factors (mainly acids produced from fermentation of sugars by oral bacteria) are brought under control via appropriate preventive measures. There are many possibilities to intervene in this continuing process to arrest or reverse the progress of the carious lesion. One possibility is behavioural intervention, such as the DR-BNI (targeting sugar intake and improving oral hygiene), which was previously shown to be successful and ENCOURAGE will develop an understanding of the mechanism of DR-BNI, to support adherence monitoring and/or caries prediction strategies.

Production of acids by oral bacteria is the main cause of enamel demineralisation and initiation of the caries process. Many organic acids are produced in this process, with lactic acid being one of the principal acids produced by oral bacteria following sugar intake, and which has been shown to correlate with caries (Gao et al., 2001; Minah & Loesche, 1997; Margolis & Moreno 1994; . Production of lactic acid requires both the presence of dental plaque (bacteria) and dietary carbohydrates in the form of sugars (source of carbon for bacterial fermentation). Lactic acid levels in saliva could therefore represent an independent surrogate for adherence to both tooth brushing (which influences abundance of plaque bacteria) and dietary sugar control (which influences amount of sugar available for bacterial fermentation).

The saliva samples will be collected at baseline (randomisation visit) and then at 6 months (+/- one month) after randomisation for both groups. Previous research has confirmed that the median timeframe for habit formation is 66 days (Lally et al., 2010). There is however likely to be fluctuation in this and there needs to be additional time allowed for behaviour changes to be embedded into daily routines, as we understand that it takes time and practice to reinforce caries prevention behaviours. Embedding these behaviours may take 2-3 months and some families may delay the start of behaviour change; by 6 months post-intervention those that are changing will have done so.

Preventing caries developing depends on consistent adoption of healthy behaviours of brushing twice daily with fluoride toothpaste and restricting sugars intake. It is these behaviours that are set as goals by parents through the intervention DR-BNI.

**11.2.2 Hypothesis:** Changes in diet (reduction in sugar consumption) and/or improved oral hygiene (tooth brushing with fluoride toothpaste twice daily and reducing dental plaque) as a result of DR-BNI behavioural intervention, may result in reduced salivary lactic acid levels. The mechanistic hypothesis is that adherence to caries prevention goals will reduce lactic acid levels in saliva by 6 months post intervention, which will then contribute towards protection against the development of caries over the two years post-intervention.

### 11.2.3 Aims and objectives

The **aim** of this research is to determine if changes in salivary acid levels and changes in the oral microbiome have a role in the mechanism of action of the DR-BNI behavioural intervention in preventing child tooth decay.

**Primary objective:** To quantify salivary levels of lactic acid at baseline, and at 6 months follow-up, and determine if change in lactic acid concentration contributes towards the effect of intervention versus control on the caries outcome at 2 years.

#### Secondary objectives:

(a) To quantify salivary levels of pyruvic acid, citric acid, 2-ketoglutamic acid, succinic acid, malic acid and fumaric acid at baseline, and at 6 months follow up, and determine if changes in these levels contribute towards the effect of intervention versus control on the caries outcome at 2 years.

(b) To determine if salivary acid levels correspond with microbiome eubiosis or dysbiosis by studying the oral bacterial microbiome and fungal mycobiome in a subset of 60 children at baseline, and at 6 months follow up.

### 11.2.4 Sample collection handling and storage:

Saliva samples will be obtained from 400 children at baseline (randomisation visit), and at 6 months (+/- 1 month) following randomisation. Saliva will be collected for approximately 5 minutes and will represent pooled salivary gland secretions, containing salivary metabolites, as well as reflecting the bacterial microbiome and fungal mycobiome. Saliva collection is a simple procedure, considered to be non-invasive. A standard operating procedure (SOP) will be developed for saliva collection, and dental nurses will be trained in saliva collection from children. Children unable to produce saliva over a 5 minute period will be excluded from the study.

Saliva samples will be frozen immediately at -20°C in small freezers. The samples will be dispatched via courier to local University freezers, regularly for storage at -80°C. Samples will subsequently be stored in line with Human Tissue Act guidelines in University freezers at -80°C until required for analysis.

### 11.2.5 Sample analysis

A full audit of saliva samples will be undertaken and the samples will be prepared for metabolomics and microbiome analysis. Following laboratory analysis, the metabolomics and microbiome data will be interpreted and the linkage of the large laboratory dataset with the outcomes of CHOICE will occur.

(i) Metabolomics: Saliva samples will be analysed by a targeted metabolomics approach by Metabolon. The dataset produced by Metabolon will be analysed in line with the microbiome data (below).

(ii) Bacterial microbiome and fungal mycobiome: Saliva samples will subsequently be analysed for their bacterial microbiome and fungal mycobiome. The DNA will be extracted from saliva in preparation of next generation sequencing. We have previous experience of microbiome analysis from clinical samples and significant expertise will be required in microbiome data analysis to interpret the raw, next generation sequencing data. The microbiome data will be analysed alongside the metabolomics data.

#### Statistical analysis

The primary analysis will be a mediation analysis using Baron & Kenny's method to test for partial mediation with a series of regression analyses. We will conclude that mediation is present if the four statements below are true:

- 1. The total of effect of DR-BNI on caries is significant
- 2. The effect of DR-BNI on lactic acid is significant
- 3. The effect of lactic acid on caries, adjusted for DR-BNI is significant
- 4. The direct of effect of DR-BNI on caries adjusted for lactic acid is reduced from the effect modelled in step 1.

The primary objective is to quantify salivary levels of lactic acid at baseline, and at 6 months follow-up, and determine if change in lactic acid concentration contributes towards the effect of intervention versus control on the caries outcome at 2 years.

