## 13.6 Analysis Plan

A full statistical analysis plan (SAP) will be written prior to the conduct of any comparative analysis of the treatment arms. The main features of the SAP are summarised below:

Participants will be included in the analysis set based on the intention-to-treat principle.

The primary outcome will be compared between groups using logistic regression, adjusted for site and baseline dental caries.

Count outcomes such as number of teeth developing caries, number of fillings and number of extractions will be compared using Poisson regression adjusted for site and baseline caries. Secondary parent reported outcomes will be analysed using linear or logistic regression, adjusted for site and baseline values.

The comparative outcomes in different ethnic groups will be explored by adding terms for ethnicity and interaction terms between ethnicity and treatment to the models of caries and oral health behaviour outcomes. This will be an exploratory analysis as we have not powered the trial to detect interactions.

An exploratory analysis will be carried out to investigate the potential mediating effects of parental self-efficacy and relief/regret on the effect of the intervention on the clinical outcome. This analysis will test for partial mediation using a series of regression analyses. We will conclude that mediation is present if the four statements below are true:

- 1. The total of effect of DR-BNI on caries is significant
- 2. The effect of DR-BNI on the mediating variable is significant
- 3. The effect of the mediating variable on caries, adjusted for DR-BNI is significant
- 4. The direct of effect of DR-BNI on caries adjusted for the mediating variable is reduced from the effect modelled in step 1.

As much information as possible will be collected about the reasons for missing outcome data; this will be used to inform any imputation approaches employed in the analysis. Such methods will be fully described in the SAP.

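### ENCOURAGE's four-step mediation rule can lose much real mediation at its total-effect gate, and leaves open the sample for step 1 and the definition of the mediator

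*Protocol*

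**What the plan says.** Protocol section 11.2.5, under the heading Statistical analysis, names a Baron and Kenny mediation analysis as the primary analysis of ENCOURAGE and fixes its decision rule: "We will conclude that mediation is present if the four statements below are true". The rule runs as follows:

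- Step 1 is a gate on the overall comparison of the arms: "The total of effect of DR-BNI on caries is significant".
- Step 2 tests the first path, from arm to mediator: "The effect of DR-BNI on lactic acid is significant".
- Step 3 tests the second path, from mediator to outcome, and names one adjustment: "The effect of lactic acid on caries, adjusted for DR-BNI is significant".
- Step 4 sets two estimates against each other and asks for no test or interval: "The direct of effect of DR-BNI on caries adjusted for lactic acid is reduced from the effect modelled in step 1".

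The objective printed directly below them is to "determine if change in lactic acid concentration contributes towards the effect of intervention versus control on the caries outcome at 2 years".

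On size, section 11.2.4 says "Saliva samples will be obtained from 400 children at baseline (randomisation visit", with a second sample at 6 months. No power is stated for the mediation analysis, and the text does not say whether step 1 is tested in the saliva children or in the whole trial.

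Section 6.1.4 lists the ENCOURAGE objectives among the exploratory and translational ones. Section 13.6 applies the same four statements to parental self-efficacy and regret/relief, as an exploratory analysis: "This analysis will test for partial mediation using a series of regression analyses".

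**The concern.** Three features of the rule deserve attention.

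- **The gate.** An indirect effect can be well estimated in a sample too small to show the total effect. Requiring a significant total effect first discards such evidence. The trial was sized for its total effect with 363 children analysed per group; the saliva set has about 200 per group before loss.
- **The mediator and step 3.** Lactic acid is not randomised. Section 11.2.1 says that it reflects plaque and dietary sugar and correlates with caries, so a child's existing habits could plausibly drive both. The steps say only lactic acid and name DR-BNI as the sole adjustment, whereas the objective speaks of change. These are different analyses with different error rates.
- **Step 4.** It compares two point estimates and attaches no uncertainty to the indirect effect, which is the quantity of interest.

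At stake is the headline conclusion of the sub-study. The main trial's primary outcome, sample size and analysis are not affected.

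**Working it through.** **Inputs from the protocol.** Section 13.2.1: 12-point difference, 90% power, alpha 0.05 (taken as two-sided), 363 per group, 20% loss, 454 per group. Section 11.2.4: 400 children, so about 200 per arm under 1:1 allocation. Applying the main trial's 20% loss to them is an assumption: 200 × 0.8 = 160 per arm. The CHOICE control rate is not stated, so several are tried.

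**The plan's own figure.** With p̄ = (p1 + p2)/2,

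n = [1.960·√(2p̄(1−p̄)) + 1.282·√(p1(1−p1) + p2(1−p2))]² / (p1 − p2)².

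For 56% v 44% this gives 362.8, so 363. For 62% v 50% it gives 358. Then 363/0.8 = 453.75, so 454 per group and 908 in total. The stated size is reproduced.

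**Power of step 1.** z = [|p1 − p2|·√n − 1.960·√(2p̄(1−p̄))] / √(p1(1−p1) + p2(1−p2)); power = Φ(z).

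| Rates | 160 per arm | 200 per arm |
|---|---|---|
| 56% v 44% | z = 0.188, 57% | z = 0.443, 67% |
| 62% v 50% | z = 0.204, 58% | z = 0.461, 68% |
| 40% v 28% | 62% | 72% |
| 30% v 18% | 71% | 80% |
| 62% v 44% (the full Dental RECUR effect) | 90% | 95% |

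At 62% v 50% with 363 or 454 per arm, power is 90% or 95%.

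**The whole rule when mediation is real.** Simulation, 1500-2000 runs per setting, all tests two-sided at 0.05. Six-month lactic acid (in SD units) = ρ·baseline + a·arm + noise; logit of caries = k + c·arm + b·(6-month lactic acid) + g·baseline; k and c set so that the total effect is 12 points. Assumed: a = −0.3 to −0.5, b = 0.3 to 0.8, ρ = 0.5, g = 0. The comparator is a joint test of the two paths (arm on lactic acid, lactic acid on caries) with baseline lactic acid in both models and no gate.

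| | 160 per arm | 200 per arm |
|---|---|---|
| Four-step rule, step 1 in the saliva children | 34-58% | 48-69% |
| Joint path test, no gate | 53-100% | 66-100% |

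The four-step rule therefore misses 31-66%. Two settings at 160 per arm show where the loss arises:

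- a = −0.5, b = 0.8: steps 2 and 3 pass in 99% and 100% of runs, step 1 in 58%. The rule declares mediation in 58%, the joint test in 99.8%. Nearly all of the loss is the gate.
- a = −0.3, b = 0.3: the rule declares mediation in 35%, the joint test in 53%. Here weak paths cost power as well.

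If step 1 is tested in the whole trial (363-454 per arm, of whom 160-200 have saliva), it fails in 4-11% of runs and the rule declares mediation in 50-94%.

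**The rule when 6-month lactic acid does nothing.** Now b = 0, a real 12-point effect arises by another route, and the arm effect on lactic acid is real. The mediator is the 6-month value with no baseline term, 200 per arm, ρ = 0.3 to 0.7.

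| Log-odds of caries per SD of baseline lactic acid (assumed) | Mediation declared |
|---|---|
| 0 | 1-2% |
| 0.3 | 8-34% |
| 0.5 | 17-61% |
| 0.8 | 33-67% |

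If the mediator is change from baseline, false declaration is 0-2%, but power under real mediation (step 1 in the saliva children) falls to 11-64%.

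**What baseline adjustment achieves.** With baseline lactic acid in the models and as the only confounder, the four-step rule falsely declares mediation in 1-2% and the joint test in 4-6%. If instead an unmeasured stable habit drives both lactic acid and caries, the four-step rule with baseline added still does so in 11-58%.

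**The case against.** The strongest points on the other side:

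- **Step 1 may be meant for the whole trial.** Section 11.2.5 speaks of linking laboratory data to the CHOICE outcomes. On that reading the gate costs little at the 12-point target. This stands as a possibility. It makes the choice of set something the protocol has to state, since the cost of the gate depends on it.
- **The objective already uses baseline.** If change is the mediator, baseline is not left out, and false declaration is rare. This also stands, but that reading pays in power.
- **Covariates belong in the statistical analysis plan.** A full covariate list does, and naming DR-BNI in step 3 does not exclude others. The decision rule and its gate, however, are fixed in the protocol.
- **A total effect is needed before asking what mediates it.** The gate also caps false declarations at the power of step 1. Reporting the total effect beside the indirect effect gives the same context without discarding the estimate.

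A reader might infer more than the document supports:

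- *That the rule often declares mediation falsely.* This needs the 6-month value without baseline, and baseline lactic acid that both predicts caries and is stable over time. The protocol gives no figure for either.
- *That the gate causes false declarations.* It causes misses.
- *That step 4 fails because logistic coefficients with and without the mediator are on different scales.* The point is correct in principle, but at a 12-point effect step 4 passed in 92% or more of the real-mediation runs at 160 per arm and cost little. Its defect is the missing interval.
- *That section 13.6 is equally underpowered.* Its questionnaires and caries outcome are planned for all 908 children, and the analysis is labelled exploratory.

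**Conclusion.** The concern holds in a limited form, as something that should be fixed in an exploratory/translational sub-study.

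- **Misses.** If step 1 is tested in the saliva children, it has 67-68% power (200 per arm) or 57-58% (160 per arm) at 12 points, and the whole rule misses about 30-65% of real mediation. Tested in the whole trial, step 1 fails only about 4-11% of the time.
- **False declarations.** The rate depends on an undefined mediator: from 1-2% to about two thirds for the 6-month value without baseline, and 0-2% for change from baseline, at a cost in power.
- **No interval.** Step 4 gives no measure of uncertainty for the indirect effect.

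The step 1 powers follow from the protocol's effect size, together with assumed control rates, a two-sided test and 20% loss. All figures for the whole rule rest on assumed path sizes, correlations and prognostic strength. The joint path test stands in for the recommended interval, which was not itself simulated.

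**What to change.** In section 11.2.5:

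- Replace the four-step rule by an estimated indirect effect on the risk-difference scale with a bootstrap 95% confidence interval. Conclude mediation if the interval excludes zero. Do not require a significant total effect, but report it alongside.
- Define the mediator as 6-month lactic acid. Put baseline lactic acid, baseline caries, age and site in both the mediator and the outcome model.
- State which children enter each estimate.
- Add a sensitivity analysis for unmeasured confounding between mediator and outcome. Baseline adjustment does not remove it, and dropping the gate removes the cap on false conclusions that the gate provided.

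For consistency, use the same estimator for the exploratory mediators in section 13.6, adjusted for the baseline score.

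The cost is analysis wording only: baseline saliva and baseline questionnaires are already scheduled. The change should be made before any comparative analysis.
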